In industrialized nations, this is a trivial requirement, as CT scans are used ubiquitously to definitively diagnose EPH and SDH, readily and reliably triaging patients to surgical versus medical management. With 97% sensitivity, 98% specificity, 97% positive predictive value, 95% negative predictive value, and 96% accuracy in diagnosing Intracranial hematomas, CT scanning is exquisitely effective at identifying or ruling out acute extra-axial, intracranial bleeds in patients who sustain head trauma, making a gold standard in acutely assessing traumatic brain injury (TBI) (2). As a result, head CT has become commonplace, if not universal in assessing head trauma in industrialized countries, where virtually every hospital has one, if not a dozen scanners. In less than 10 minutes, a CT scan can noninvasively prove or reject acute intracranial bleeding. They

provide immediate insight into 1.) Whether there is in fact an intracranial bleed; 2.) In the case of a bleed, where below the cranium it has occurred and 3.) When done serially, gauge evolution, resolution, or stability of a bleed. This is invaluable information that directly impacts survival, as failure to perform a craniotomy in a patient with a rapidly expanding intracranial hematoma can swiftly lead to irreversible brain damage or even death. Moreover, performing such a surgery in the wrong location or in a patient who does not have a bleed amenable to surgical intervention can contribute extensive morbidity, exacerbating a patient's already tenuous mortality.

In less developed countries, CT scanners are often nonexistent. When they are present, they are extremely meager in number, peppered across treacherous geography, with scant transportation and emergency infrastructure. Even when accessible, they are commonly decommissioned due to a broken part, and are extremely cost prohibitive, with a single scan often costing the equivalent to multiple months' income for the populations who need them most. As a consequence, in the settings where TBI pervades and brain imaging is most critical to survival, obtainment of such imaging is often unachievable.

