procedure will be explained in detail, using an IRB-approved verbal consent “script”, with all questions answered to the patient’s and/or representative’s satisfaction. Because patients who sustain head trauma injuries typically remain within the hospital for multiple days for monitoring and care, each participant may undergo multiple CT scans over the course of his or her hospitalization, affording the opportunity to one to numerous measurements from each patient during his or her hospital stay. When subjects are approached for subsequent study measurements, if the subject has regained the capacity to consent or has an LAR present, the verbal script will be used to obtain consent. Subjects will be asked at that time if prior measurements obtained may be used in the research.

Within 30 minutes following each CT scan, the study team will approach the patient to scan the patient’s cranium with the InfraScanner 2000™ (Image A). The procedure will entail placing 8 plastic light guides upon the patient’s scalp. The study team member will use the device to sequentially emit light through each of the 8 light guides so that the light is incident upon scalp (Image B). The device is engineered such that the light emitter and receiver are spaced ~4cm apart, allowing the light’s intensity to be measured between adjacent light guides (Image C). This entire procedure, including greeting the patient, placing the light guides, gathering the data, and removing the light guides should take ~10 minutes each time. The number of CT scans the patient receives determines the number of potential data collections. The patient will be approached by the study team following each CT scan to be scanned with the InfraScanner 2000™ (20). The patient and/or representative may refuse a scan during any encounter, and as such, the scan will not be done. For each patient scanned with the InfraScanner 2000™ they will be de-identified with a subject number, with age, sex, gender, skin color, hair color, hair thickness, mechanism of injury, Glasgow Coma Scale score, and mean time elapsed between CT scan and near-infrared measurement. These data will be stored in de-identified form on Research Electronic Data Capture (REDCap), Duke Box, and/or Microsoft Excel 2016 on a secured DHTS server (S:\NSU_IRB\Pro00087011).

The collection period for each research subject concludes 30-days following his or her initial measurement with the InfraScanner 2000™, patient discharge, or patient death.

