- 13. Statistical Considerations:** Objectives: The primary objective of this study is to estimate the test characteristics (sensitivity, specificity, and the false positive and false negative rates) of the portable NIR-based device (InfraScanner 2000™) in the identification of any size hematoma among patients hospitalized at DUH who have sustained or who are suspected to have sustained head trauma and have consequently received a brain CT scan(s). The results of the CT scan(s) will serve as the gold standard. The sensitivity, specificity, and the false positive and

false negative rates will be estimated at the patient level and at the scan level. Approximately 90% of patients are expected to have more than one CT scan.

A secondary objective is to estimate the test characteristics of the InfraScanner 2000™ in identification of hematomas within its detection limits (volume >3.5 mL and depth <2.5 cm) compared to CT scan results as the gold standard.

Exploratory objectives include:

1. Examining the impact of factors such as hematoma type, location, and patient age on test characteristics of the InfraScanner 2000™
2. Determining the minimum resolution detectable by the InfraScanner 2000™
3. Estimating Receiver Operating Characteristic (ROC) curves with patient and scan as the units of analysis (21).

Study Design:

a) Eligibility:

Any patient who presents to DUH with suspected head trauma and receives a brain CT scan will be considered for this study. Based on previously reported data, we expect that SDH or EDH will be present in approximately 20% of patients overall.

b) Standard of comparison:

All patients entered onto the trial will undergo at least one cranial scanning using the InfraScanner 2000™ within 30 minutes of CT. Patients will be scanned using the InfraScanner 2000™ within 30 minutes of each subsequent CT. Patients will know the results of the CT but not the InfraScanner 2000™. The standard for comparison will be determined as follows. A CT result that is positive for hematoma will be considered a true positive and a CT result that is negative for hematoma will be considered a true negative. In cases where the results of the CT are negative for hematoma and the results of the InfraScanner 2000™ are positive consideration of further follow-up will be given on a case-by-case basis.

Definitions of Sensitivity, Specificity, False Positive, False Negative

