**Study Population:**

- Any patient who presents to DUH with suspected head trauma and receives a brain CT scan will be considered for this study. Our final sample size is 581 measurements for 500 patients.

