### **Statistical Analysis:**

#### **Definitions of the statistics of interest:**

Let A+ denote the event that the test is positive for hematoma and B+ denote the event that a hematoma is present. Sensitivity,  $P(A+/B+)$ , will be defined for each patient (scan) as the probability that a true hematoma as determined by CT scan will be detected (14). Similarly, let A- denote the event that the test is negative for hematoma and B- denote the event that a hematoma is not present. Specificity,  $P(A-/B-)$ , will be defined as the probability of being negative for hematoma on the InfraScanner 2000™ scan within 30 minutes of CT given the patient has no hematoma present.

The false positive rate will be defined as  $PF+ = P(B-/A+) = P(A+/B-)[1-P(B+)]/P(A+)$ . Similarly, the false negative rate will be defined as  $PF- = P(B+/A-) = [1-P(A+/B+)]P(B+)/[1-P(A+)]$ . Estimates for the false positive and false negative rates will be provided for a range of values for the prevalence of hematomas.

1. Estimation of test characteristics with 90% confidence at the patient level using SAS 9.4;
2. Estimate test characteristics at the scan level (treat each measurement as independent sample) and 95% confidence intervals will be computed as a secondary analysis.
3. Estimating Receiver Operating Characteristic (ROC) curves with patient and scan as the units of analysis with 95% confidence interval.
4. Fit a logistics regression of correct and incorrect detection from InfraScanner, adjusting for age, gender, skin color, hair color, hair thickness, hair length, scalp hematoma, scalp laceration, scalp fracture, ventricular effacement and midline shift.

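### The scan-level analysis treats 581 pairs from 500 patients as independent and equally weighted, although pairs per patient follow the number of CTs received

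*Protocol*

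**What the plan says.** Protocol section 4 (Design and Procedures) expects that "each participant may undergo multiple CT scans over the course of his or her hospitalization", and states: "The number of CT scans the patient receives determines the number of potential data collections". Section 9 (Study Interventions) repeats this. Collection has an end point: "The collection period for each research subject concludes 30-days following his or her initial measurement", or at discharge or death. Not every CT yields a pair: "The patient and/or representative may refuse a scan during any encounter", and section 9 requires a measurement only when feasible.

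Under the primary objective in Protocol section 13, sensitivity, specificity and the "false negative rates will be estimated at the patient level and at the scan level", with no ranking of the two levels. The SAP, Statistical Analysis, item 2 reads "Estimate test characteristics at the scan level (treat each measurement as independent sample"), with 95% intervals, and calls this secondary. Analysis plan items 3 to 7 repeat each 2x2 analysis at scan level. SAP, Study Population, reports: "Our final sample size is 581 measurements for 500 patients". Neither document gives a per-patient weight, a cluster method or a first-pair analysis.

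**The concern.** Several scans of one head share the same skull, hair, scalp and often the same bleed, so their results are unlikely to be independent. Intervals that assume independence are too narrow when results within a patient are positively correlated.

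Equal weight per pair also means that a patient with four pairs counts four times. Protocol section 13 gives the device's detection limits in volume and depth, and section 10 says that higher optical density indicates a larger hematoma, so detectability depends on the bleed. Section 2 describes what CT scans offer: "When done serially, gauge evolution, resolution, or stability of a bleed". If patients with particular bleeds are re-imaged more often, the scan-level estimate moves away from the per-patient average, in a direction that cannot be known in advance. A cluster-robust interval repairs the width but leaves the point estimate where it is.

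The patient-level analysis is not a neutral check on this. Under SAP, Data Management, a patient with several scans is classified by the first device-positive assessment, so more scans give more chances of a positive result.

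**Working it through.** **The plan's own figures.** At 13% prevalence, 68/0.13 = 523.1 (stated 523) and 523 − 68 = 455. The half-widths are 1.645 × √(0.25/68) = 0.0997 (stated 0.099) and 1.645 × √(0.25/455) = 0.0386 (stated 0.038). They reproduce, apart from truncation. They concern patients; no precision is planned for scans.

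**Repeats.** 581 − 500 = 81 repeat pairs, a mean of 581/500 = 1.162 pairs per patient. At most 81/500 = 16.2% of patients have more than one pair.

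**Interval width.** Let m be a patient's number of pairs and ρ the within-patient correlation. For the unweighted proportion, the independence variance must be multiplied by 1 + (Σm²/Σm − 1)ρ.
- If 81 patients have two pairs each, Σm²/Σm = (419 + 81 × 4)/581 = 743/581 = 1.279. At the extreme ρ = 1, intervals should be √1.279 = 1.13 times as wide.
- If all 81 repeats fall in 65 CT-positive patients, as evenly as possible (49 with two pairs, 16 with three), Σm²/Σm = (49 × 4 + 16 × 9)/146 = 340/146 = 2.33. At ρ = 1 the sensitivity interval should be √2.33 = 1.53 times as wide.

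A smaller ρ gives less; repeats concentrated in fewer patients give more.

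**Point estimate.** If p is a patient's detection probability, the scan-level estimate minus the patient average is Cov(m, p)/mean(m). To illustrate, assume:
- 0.13 × 500 = 65 CT-positive patients (the interim prevalence, applied to the final 500);
- half detected with probability 0.95 and half with 0.60, so the patient average is 0.775;
- x repeats among CT-positive patients, a share q of them in the easier half.

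The shift is then 0.35 × x × (q − 0.5)/(65 + x).

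| Allocation of repeats | x | q = 1 | q = 0.75 |
|---|---|---|---|
| Spread evenly over patients (81 × 0.13) | 10.5 | +2.4 points | +1.2 points |
| CT-positives at twice the rate (81 × 130/565) | 18.6 | +3.9 | about +2 |
| About half of all repeats in CT-positives | 40 | +6.7 | +3.3 |
| All repeats in CT-positives | 81 | +9.7 | +4.9 |

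The bottom row at q = 1 is (113.5 × 0.95 + 32.5 × 0.60)/146 = 0.872. Putting all repeats in the harder half reverses the sign: 0.678, or −9.7 points.

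**Specificity, same kind of split.** With 435 CT-negative patients and all 81 repeats among them, all in one half, the shift is 0.35 × 81 × 0.5/(435 + 81) = 2.7 points.

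**A second model.** Suppose instead that re-imaged patients differ from single-pair patients by a gap d. The shift is (w − f) × d, where f is the re-imaged fraction of patients and w their share of pairs. With d from 0.2 to 0.4 and one to five extra pairs per re-imaged patient, sensitivity shifts by 2.3 to 5.4 points if repeats are spread evenly and by 3.2 to 8.4 if CT-positives are re-imaged at twice the rate. Specificity shifts by 2.3 to 6.0. The result depends on the assumed model as much as on the counts.

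**The case against.** Four objections carry weight.

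First, the unweighted proportion is a valid estimate of accuracy per scan performed. It is off target only if the target is accuracy per patient. This stands: the estimate should be labelled, not discarded.

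Second, the link between re-imaging and the bleed is inferred. The remark on serial CT in Protocol section 2 is general background, and section 4 attributes repeat CTs to multi-day stays after head trauma. Section 13 expects about 90% of patients to have more than one CT and about 20% to have a hematoma, so at least 70% were expected to be hematoma-free and re-imaged. With at most 16.2% contributing repeat pairs, pair counts may largely reflect refusal and feasibility. This also stands, and it makes the bottom row of the table unlikely.

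Third, a reader might infer that Aim 2 concerns a patient scanned once, so that the per-scan estimate misses its purpose. The documents do not say so: Protocol sections 2 and 3 describe repeated and sequential use of the device, for which per-scan accuracy is relevant.

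Fourth, the SAP calls the scan-level analysis secondary, and the ±0.10 precision target applies to patients. Both limit the weight of the point, although the protocol lists scan level under its primary objective.

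None of this rescues the independence assumption, which has no support for repeat scans of one patient.

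**Conclusion.** The point holds in a limited form. Treating 581 pairs from 500 patients as independent ignores within-patient correlation, and equal weighting makes the estimate a per-scan quantity that the plan does not label as such. Whether it departs from the per-patient average depends on the split of repeats and the accuracy gap, and the documents give neither.

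Under the 0.95/0.60 split with 65 CT-positive patients, the sensitivity shift is about 1 to 4 points for an even spread or a doubled re-imaging rate. A reader might infer from the extreme case that scan-level estimates are wrong by up to 10 points. The documents do not support that. Under this split it requires all 81 repeats in one detectability half of the CT-positive patients. Ten points is neither a bound nor an expected value, since other assumed models give smaller or larger shifts. Specificity is expected to move less: at most 2.7 points under the same kind of split. Severity is low to moderate.

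**What to change.** In SAP, Statistical Analysis, item 2, and in the scan-level repeats of Analysis plan items 3 to 7:
- Replace the independence assumption with an analysis that uses patient as the cluster, for example SAS PROC SURVEYFREQ with a CLUSTER statement.
- Keep the unweighted scan-level estimate and label it as accuracy per scan performed.
- Beside it, as a sensitivity analysis, report an estimate that weights each pair by 1/(that patient's pairs with the same CT status), or one that uses each patient's first pair only. The two answer different questions: the weighted one averages over the hospital course, and the first-pair one describes the entry scan. The SAP should say which is meant.
- Tabulate pairs per patient by CT status, so that readers can judge how unevenly the repeats fell.

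The cost is SAP wording, a patient identifier as cluster and one weight variable. No new data are needed. The downside is somewhat wider scan-level intervals.

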Let A^+ denote the event that the test is positive for hematoma and B^+ denote the event that a hematoma is present. Sensitivity, $P(A^+/B^+)$, will be defined for each patient (scan) as the probability that a true hematoma as determined by CT scan will be detected (22). Similarly, let A^- denote the event that the test is negative for hematoma and B^- denote the event that a hematoma is not present. Specificity, $P(A^-/B^-)$, will be defined as the probability of being negative for hematoma on the InfraScanner 2000™ scan within 30 minutes of CT given the patient has no hematoma present.

The false positive rate will be defined as $P_{F+} = P(B^-/A^+) = P(A^+/B^-)[1 - P(B^+)]/P(A^+)$. Similarly, the false negative rate will be defined as $P_{F-} = P(B^+/A^-) = [1 - P(A^+/B^+)]P(B^+)/[1 - P(A^+)]$. Estimates for the false positive and false negative rates will be provided for a range of values for the prevalence of hematomas.

c) Sample Size

Computation of the required number of patients is based on estimating the sensitivity of each method to within at most ± 0.10 with 90% confidence. The 90% confidence interval for the sensitivity is given by $P_{Sens} \pm 1.645 * SE(P_{Sens})$ where $SE(P_{Sens}) = \sqrt{(P_{Sens})(1 - P_{Sens})/N}$; N denotes the number of true positives.

Administrative Summary: Based on an interim analysis conducted after 200 patients were studied, the proportion of patients with hematomas is 0.13. This is lower than the 20% originally expected. The sample size computation was thus revised as follows.

Original sample size computation

With 68 patients with positive findings of hematoma, sensitivity can be estimated to within at most ± 0.099 with 90% confidence. Assuming 20% of patients have true hematomas detected, 340 patients must be accrued (10). Allowing for a 5% dropout rate the required sample size for this trial is 360 subjects. With 272 patients having negative findings for hematoma, specificity can be estimated to within at most ± 0.05 with 90% confidence.

Revised sample size computation

With 68 patients with positive findings of hematoma, sensitivity can be estimated to within at most ± 0.099 with 90% confidence. Assuming 13% of patients have true hematomas detected, 523 patients must be enrolled to observe positive findings in 68 patients. With 455 patients having negative findings for hematoma, specificity can be estimated to within at most ± 0.038 with 90% confidence.

d) Interim Analysis

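### The revised target of 523 patients has no slack and no dropout allowance, and at the SAP's final 500 the worst-case guarantee of ±0.10 for sensitivity is narrowly lost without the precision being restated

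*Protocol*

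**What the plan says.** Protocol section 13, c) Sample Size, bases the number of patients on "estimating the sensitivity of each method to within at most ± 0.10 with 90% confidence". The interval is the usual normal approximation with multiplier 1.645, and "N denotes the number of true positives".

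The Administrative Summary reports that, after 200 patients, "the proportion of patients with hematomas is 0.13", against the 20% planned. The revised computation keeps the same requirement: "With 68 patients with positive findings of hematoma, sensitivity can be estimated to within at most ± 0.099 with 90% confidence". It then assumes 13% and concludes that "523 patients must be enrolled to observe positive findings in 68 patients". For the 455 patients left as negatives, "specificity can be estimated to within at most ± 0.038 with 90% confidence". The computation it replaces went from 340 to 360 patients to allow for 5% dropout. The revised one has no such step and gives no reason for leaving it out.

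The SAP, under Study Population, states: "Our final sample size is 581 measurements for 500 patients". It does not give the number of CT-positive patients, mention 523, or restate the half-widths.

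**The concern.** The half-width for sensitivity depends on how many patients turn out CT-positive, and that number is random. The protocol fixes the smallest count that meets ±0.10 and divides it by an interim proportion taken as a point value, so any shortfall in positives breaks the guarantee. The final sample is 23 patients below the number that the protocol says must be enrolled.

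The study's primary objective is estimation, and this is the only quantitative justification for its size. If the figures are left as they stand, a reader of the two documents will credit the study with a worst-case precision that its final sample is not expected to support.

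**Working it through.** **Inputs.** From protocol section 13 c): target ±0.10, multiplier 1.645, prevalence 0.13 from 200 patients (0.13 × 200 = 26 positives), 68 positives, 455 negatives, 523 patients, and 5% dropout in the earlier computation. From the SAP: 500 patients.

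**The plan's own figures.** The formula is 1.645 × √(p(1−p)/N). The printed bounds arise at the worst case p = 0.5, where it becomes 0.8225/√N.
- Smallest N for ±0.10: 0.25 × 1.645² / 0.10² = 67.65, so 68.
- N = 68: 0.0997. N = 67: 0.1005. There is no slack.
- N = 455: 0.0386.
- Enrolment: 68/0.13 = 523.08, printed as 523. Expected positives: 523 × 0.13 = 67.99.

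The plan's figures therefore reproduce, except that 0.0997 and 0.0386 are printed as upper bounds of 0.099 and 0.038. Both are slightly too small for a bound.

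**Enrolment step.** With X ~ Binomial(523, 0.13), P(X ≥ 68) = 0.519. Given 26 positives already seen in 200, it is 0.524. Allowing also for uncertainty in the prevalence (beta-binomial, Jeffreys prior) it is 0.523. A 5% loss from 523 leaves 523 × 0.95 × 0.13 = 64.6 expected positives. Restoring the allowance would have given 523/0.95 = 550.5, so 551.

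**Final sample of 500.** At 13%:
- Expected positives are 65, with worst-case half-width 0.8225/√65 = 0.1020.
- Expected negatives are 435, with worst-case half-width 0.8225/√435 = 0.0394.
- P(X ≥ 68) = 0.364. Given 26/200 it is 0.33 with prevalence held at 13%, and 0.40 with prevalence uncertain.
- The 90% predictive range, given 26/200, is 51 to 82 positives, that is ±0.115 to ±0.091.

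**When ±0.10 is actually exceeded at 65 positives.** This needs p(1−p) > 65 × (0.10/1.645)² = 0.2402, so p between 0.401 and 0.599. Outside that range the target is met:

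| Estimated sensitivity | Half-width at 65 positives |
|---|---|
| 0.50 | 0.102 |
| 0.60 | 0.100 |
| 0.70 | 0.094 |
| 0.80 | 0.082 |
| 0.88 | 0.066 |

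**Chance that the reported half-width is within ±0.10.** This lets both the number of positives and the estimated sensitivity vary, at prevalence 0.13:

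| True sensitivity | 500 patients | 523 patients |
|---|---|---|
| 0.50 | 0.41 | 0.57 |
| 0.70 | 0.82 | 0.89 |
| 0.80 | 0.98 | 0.99 |
| 0.88 | 0.999 | 1.00 |

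**The case against.** The strongest reply is that little is lost. The excess at 65 positives is 0.002 on a target of ±0.10, in a self-described pilot with no test, margin or decision threshold hanging on it. The protocol labels 13% as an assumption, and planning on expected counts is common. An 80% assurance of 68 positives would have taken 572 patients at exactly 13%, but nothing in the documents commits to an assurance level. The SAP already promises confidence intervals, so the achieved precision will be visible. All of this stands, and it limits the point to a correction of wording.

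Three stronger readings are tempting, and the documents do not support them.
- **That the trial will probably miss ±0.10.** The interval uses the estimated sensitivity, so a miss at 65 positives needs an estimate near one half. With 523 patients, reaching 68 positives is slightly more likely than not.
- **That the bounds of ±0.099 and ±0.038 rest on 13% prevalence.** Each is conditional on a count, 68 or 455. Prevalence enters only in the step from 68 positives to 523 patients.
- **That specificity is at risk from the prevalence estimate.** Its worst-case half-width stays between about 0.038 and 0.041 for prevalence 0.09 to 0.20 at either sample size.

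The reply does not remove the whole point. The plan assumes no value for sensitivity and chose a worst-case bound, so it should be judged on that bound. The 88% quoted in the background is for the earlier device model and for hematomas within its detection limits, whereas the primary objective covers hematomas of any size with the newer model. The gap between 523 and 500, the missing dropout allowance and the truncated bounds do not depend on the sensitivity at all.

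**Conclusion.** The point holds in a limited form. The revised enrolment figure is an expected-value calculation with about a 52% chance of delivering 68 positives at 13% prevalence, and it omits a dropout allowance that the plan had used before. At 500 patients the expected worst-case half-width for sensitivity is ±0.102, so the guarantee of ±0.10 whatever the sensitivity no longer holds. The loss is small and matters only for an estimated sensitivity of about 0.40 to 0.60. The two truncated bounds are wrong by less than 0.001.

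This rests on three assumptions. First, prevalence among the 500 is taken as 13%, because the CT-positive count is not given; 68 or more positives would restore the guarantee. Second, 500 is taken as the number of patients analysed. The documents do not say whether the 23 missing patients (23/523 = 4.4%) reflect losses or earlier closure. Third, the 90% level of the sample size section is used. The SAP names 90% for patient-level estimates in one list and 95% in its Analysis plan. At 95% the worst case would be 0.119 with 68 positives and 0.122 with 65.

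**What to change.** No added enrolment is needed.

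1. In protocol section 13 c), change the bounds to ±0.100 for 68 positives (in both computations) and ±0.039 for 455 negatives.
2. In the SAP, under Study Population, add wording such as: With 500 patients and a prevalence of 13%, about 65 CT-positive and 435 CT-negative patients are expected. The worst-case 90% half-width is ±0.102 for sensitivity (about ±0.091 to ±0.115 over 82 to 51 positives) and ±0.039 for specificity.
3. Reconcile 523 with 500: say whether the difference is dropout or a decision to stop, and why the 5% allowance was left out of the revision.
4. In the results, report the actual number of CT-positive patients and the half-width achieved.

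The cost is a few sentences. The only downside is that the stated precision becomes slightly less favourable.
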